### **3.5 Discontinuation of Subjects following any Treatment with Study Drug**

Subjects MUST discontinue investigational product (and non-investigational product at the discretion of the investigator) for any of the following reasons:

- Subject's request to stop study treatment
- Any clinical AE, laboratory abnormality or intercurrent illness which, in the opinion of the investigator, indicates that continued participation in the study is not in the best interest of the subject
- Termination of the study by Bristol-Myers Squibb (BMS)
- Loss of ability to freely provide consent through imprisonment or involuntarily incarceration for treatment of either a psychiatric or physical (eg, infectious disease) illness
- Pregnancy
- Additional protocol specific reasons for discontinuation (see [Sections 4.5.3.1](#) and [4.5.3.2](#))

All subjects who discontinue study drug should comply with protocol specified follow-up procedures as outlined in [Section 5](#). The only exception to this requirement is when a subject withdraws consent for all study procedures including post-treatment study follow-up or loses the ability to consent freely (ie, is imprisoned or involuntarily incarcerated for the treatment of either a psychiatric or physical illness).

If study drug is discontinued prior to the subject's completion of the study, the reason for the discontinuation must be documented in the subject's medical records and entered on the appropriate case report form (CRF) page.

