#### **4.5.1.2 Nivolumab Dose Delay**

Investigators should, whenever possible, determine which medication is causing the toxicity and delay or dose reduce ulocuplumab and/or delay nivolumab, as applicable. If nivolumab is delayed due to an AE, ulocuplumab dosing should also be delayed. Nivolumab should be delayed for the following:

- Any Grade  $\geq 2$  non-skin, drug-related AE, with the following exceptions:
  - Grade 2 drug-related fatigue or laboratory abnormalities do not require a treatment delay
- Any Grade 3 skin drug-related AE
- Any Grade  $\geq 3$  drug-related laboratory abnormality, with the following exceptions for thrombocytopenia, lymphocytopenia, AST, ALT, total bilirubin or asymptomatic amylase or lipase:
  - Grade 3 thrombocytopenia  $< 7$  days (not associated with Grade  $\geq 2$  hemorrhage) does not require dose delay
  - Grade 3 lymphocytopenia not associated with symptoms or clinical manifestations does not require dose delay. It is recommended to consult with the BMS Medical Monitor for Grade 3 lymphocytopenia.
  - Grade 3 drug-related amylase or lipase abnormality that is not associated with symptoms or clinical manifestations of pancreatitis does not require dose delay. It is recommended to consult with the BMS Medical Monitor for Grade 3 amylase or lipase abnormalities
  - If a subject has baseline AST, ALT, or total bilirubin that is within normal limits, delay dosing for drug-related Grade  $\geq 2$  toxicity
  - If a subject has baseline AST, ALT, or total bilirubin within the Grade 1 toxicity range, delay dosing for drug-related Grade  $\geq 3$  toxicity
  - If a subject has baseline AST or ALT within the Grade 2 toxicity range, delay dosing for drug-related elevations in AST and/or ALT  $> 2x$  baseline or a maximum of  $> 8x$  ULN
- Any adverse event, laboratory abnormality, or intercurrent illness which, in the judgment of the investigator, warrants delaying the dose of study medication

If the decision is to resume nivolumab dosing, the subject should restart treatment on the next regularly scheduled nivolumab dosing visit. Skipped doses are not to be replaced. If treatment is delayed  $> 6$  weeks, the subject must be permanently discontinued from all study therapy, except as specified in [Section 4.5.3.2](#).

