### **4.5.1.3 Criteria to Resume Nivolumab Treatment**

Subjects may resume treatment with nivolumab when the drug-related AE resolves to Grade  $\leq$  1 or baseline value, with the following exceptions:

- Subjects may resume treatment in the presence of Grade 2 fatigue
- Subjects who have not experienced a Grade 3 drug-related skin AE may resume treatment in the presence of a Grade 2 toxicity
- Subjects with baseline AST/ALT or total bilirubin in the Grade 1 or 2 toxicity range who require dose delays for reasons other than a 1 or 2-grade shift in AST/ALT or total bilirubin may resume treatment in the presence of Grade 2 AST/ALT OR total bilirubin
  - Subjects with combined Grade 2 AST/ALT AND total bilirubin values meeting discontinuation parameters ([Section 4.5.3.2](#)) should have treatment permanently discontinued
- Drug-related pulmonary toxicity, diarrhea, or colitis must have resolved to baseline before treatment is resumed
- Drug-related endocrinopathies adequately controlled with only physiologic hormone replacement may resume treatment

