#### **4.5.3.2 Nivolumab Discontinuation Criteria**

Discontinuation criteria apply for all drug-related AE attributed to nivolumab and consist of the following:

- Any Grade 2 drug-related uveitis, eye pain, or blurred vision that does not respond to topical therapy and does not improve to Grade 1 severity within the re-treatment period OR requires systemic treatment
- Any Grade 3 non-skin, drug-related adverse event lasting  $> 7$  days, with the following exceptions for drug-related laboratory abnormalities, uveitis, pneumonitis, bronchospasm, diarrhea, colitis, neurological toxicity, hypersensitivity reactions, and infusion reactions:
  - Grade 3 drug-related uveitis, pneumonitis, bronchospasm, diarrhea, colitis, neurologic toxicity, hypersensitivity reaction, or infusion reaction of any duration requires discontinuation
  - Grade 3 drug-related endocrinopathies adequately controlled with only physiologic hormone replacement do not require discontinuation
  - Grade 3 drug-related laboratory abnormalities do not require treatment discontinuation except:
    - ◆ Grade 3 drug-related thrombocytopenia associated with bleeding requires discontinuation
    - ◆ Any drug-related liver function test (LFT) abnormality that meets the following criteria require discontinuation:
      - If a subject has a baseline AST or ALT within normal limits:
        - AST or ALT  $> 5-8x$  ULN for  $> 2$  weeks
        - AST or ALT  $> 8x$  ULN, irrespective of duration
        - Concurrent AST or ALT  $> 3x$  ULN and total bilirubin  $> 2x$  ULN
      - If a subject has a baseline AST or ALT within Grade 1 or 2 toxicity range:
        - AST or ALT  $> 10x$  ULN for  $> 2$  weeks
        - AST or ALT  $> 15x$  ULN, irrespective of duration
        - Total bilirubin  $> 5x$  ULN
        - Concurrent AST or ALT  $> 3x$  ULN and total bilirubin  $> 2x$  ULN

- Any Grade 4 non-skin drug-related adverse event or laboratory abnormality, except for the following events which do not require discontinuation:
  - Isolated Grade 4 electrolyte imbalances/abnormalities that are not associated with clinical sequelae and are corrected with supplementation/appropriate management within 72 hours of their onset
  - Grade 4 thrombocytopenia or neutropenia < 5 days
  - Grade 4 lymphocytopenia or leukopenia not associated with symptoms or clinical manifestations. It is recommended to consult with the BMS Medical Monitor for Grade 4 lymphocytopenia.

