  - Grade 4 amylase or lipase abnormalities that are not associated with symptoms or clinical/radiographic manifestations of pancreatitis. It is recommended to consult with the BMS Medical Monitor for Grade 4 amylase or lipase abnormalities.
  - Grade 4 drug-related endocrinopathy adverse events, such as adrenal insufficiency, ACTH deficiency, hyper- or hypothyroidism, or glucose intolerance, which resolve or are adequately controlled with physiologic hormone replacement (corticosteroids, thyroid hormones) or glucose-controlling agents, respectively, may not require discontinuation after discussion with and approval from the Medical Monitor.
- Any dosing delay lasting > 6 weeks with the following exceptions:
  - Dosing delays to allow for prolonged steroid tapers to manage drug-related AEs are allowed. Prior to re-initiating treatment in a subject with a dosing delay lasting > 6 weeks, the BMS Medical Monitor must be consulted. Tumor assessments should continue as per protocol even if dosing is delayed.
  - Dosing delays > 6 weeks that occur for non-drug-related reasons may be allowed if approved by the BMS Medical Monitor. Prior to re-initiating treatment in a subject with a dosing delay lasting > 6 weeks, the BMS Medical Monitor must be consulted. Tumor assessments should continue as per protocol even if dosing is delayed.
- Any adverse event, laboratory abnormality, or intercurrent illness which, in the judgment of the Investigator, presents a substantial clinical risk to the subject with continued ulocuplumab or nivolumab dosing

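### Protocol 4.5.3.2 stops nivolumab for total bilirubin above 5x ULN when baseline AST/ALT is Grade 1-2 but omits that line for normal baseline: a narrow safety gap that one line closes

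*Protocol*

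**What the plan says.** Protocol 4.5.3.2 starts from a lenient default for laboratory values: "Grade 3 drug-related laboratory abnormalities do not require treatment discontinuation except" for bleeding-associated thrombocytopenia and for a set of liver-test results. The liver results are split by baseline enzymes.

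- Under "If a subject has a baseline AST or ALT within normal limits" there are three triggers: AST/ALT above 5-8x ULN for more than 2 weeks; AST/ALT above 8x ULN at any duration; and AST/ALT above 3x together with total bilirubin above 2x ULN.
- Under "If a subject has a baseline AST or ALT within Grade 1 or 2 toxicity range" there are four: AST/ALT above 10x ULN for more than 2 weeks; AST/ALT above 15x ULN at any duration; total bilirubin above 5x ULN; and the same combined enzyme-and-bilirubin rule.

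The same section separately requires discontinuation for "Any Grade 4 non-skin drug-related adverse event or laboratory abnormality, except for the following events which do not require discontinuation". Bilirubin is not among those exceptions. It also leaves a general discretion to stop for anything that, "in the judgment of the Investigator, presents a substantial clinical risk to the subject with continued ulocuplumab or nivolumab dosing".

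**The concern.** The lists are split on AST/ALT, but the line that differs concerns bilirubin. It also runs against the pattern of the neighbouring rules, where normal-baseline subjects get the tighter limit. Protocol 4.5.1.2 holds nivolumab at Grade 2 or above when baseline AST, ALT or bilirubin was normal, but at Grade 3 or above when it was Grade 1. Protocol 4.5.1.3 relaxes the restart rule for liver tests only for abnormal baselines. Both enzyme limits in 4.5.3.2 are lower for normal baselines.

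What is at stake is re-exposure. The same drug-related, isolated bilirubin rise permanently ends nivolumab in a subject who entered with raised enzymes. In a subject who entered with normal enzymes, nivolumab may be restarted. Sites also face two signals: 4.5.3.2 does not require a stop above 5x ULN for the second subject, while Appendix 2 offers delay only up to 5x ULN.

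**Working it through.** The plan states no figure to reproduce. The check sets the mandatory rules side by side and finds where they give different answers.

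**Inputs.** The stopping rules are from Protocol 4.5.3.2 and the hold and 6-week rules from 4.5.1.2. Restart is from 4.5.1.3, the entry limit from 3.3.1 and the hepatic footnote from Appendix 2. I take normal baseline to mean that both enzymes were normal.

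| Mandatory nivolumab stop | Normal baseline AST/ALT | Grade 1-2 baseline AST/ALT |
|---|---|---|
| AST/ALT, more than 2 weeks | > 5-8x ULN | > 10x ULN |
| AST/ALT, any duration | > 8x ULN | > 15x ULN |
| AST/ALT > 3x with bilirubin > 2x ULN | yes | yes |
| Bilirubin > 5x ULN alone | **absent** | **yes** |
| Grade 4 bilirubin | yes | yes |
| Delay > 6 weeks (limited exceptions) | yes | yes |

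**Step 1: enzymes.** At any bilirubin above 5x ULN, AST/ALT above 3x ULN triggers the combined rule in both groups. Take bilirubin 6x ULN and an assumed Grade 4 cut-off of 10x. At AST/ALT 1x, 2x or 3x, only the Grade 1-2 group must stop. At 3.1x or 6x, both must. The gap therefore needs AST/ALT at or below 3x ULN.

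**Step 2: upper edge.** Grade 4 bilirubin stops both groups. The documents do not state where Grade 4 starts, so the range is shown.

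| Assumed Grade 4 bilirubin cut-off | Bilirubin range where the groups differ (AST/ALT ≤ 3x ULN) |
|---|---|
| > 5x ULN | none |
| > 6x ULN | above 5x to 6x |
| > 8x ULN | above 5x to 8x |
| > 10x ULN | above 5x to 10x |
| > 15x ULN | above 5x to 15x |

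The line sits among the exceptions to the Grade 3 default, and Grade 4 is handled separately. It adds something only if bilirubin can exceed 5x ULN while below Grade 4. That favours a cut-off above 5x but does not prove it.

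**Step 3: time.** Nivolumab is held during the event, and "If nivolumab is delayed due to an AE, ulocuplumab dosing should also be delayed". "Subjects may resume treatment with nivolumab when the drug-related AE resolves to Grade" 1 or below, or to baseline. A delay beyond 6 weeks ends treatment in both groups. For a drug-related event the relevant exception is a prolonged steroid taper, with the sponsor's Medical Monitor consulted before any restart. The gap is thus confined to events that recover within 6 weeks or fall under an exception.

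**Step 4: entry bilirubin.** Protocol 3.3.1 requires total bilirubin at or below 1.5x ULN whatever the AST/ALT (Gilbert syndrome excepted). Reaching 5x ULN is at least a 5 / 1.5 = 3.3-fold rise in either group, so a different bilirubin starting point does not explain the split.

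**Step 5: Appendix 2.** The hepatic footnote allows delay in place of discontinuation at AST/ALT up to 8x and bilirubin up to 5x ULN. Within 4.5.3.2, 8x is the any-duration enzyme limit of the normal-baseline list only. The footnote pairs it with the bilirubin limit which that list lacks.

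**Step 6: other consequences.** Protocol 3.1.4 already counts a drug-related Grade 3 or higher bilirubin as a DLT when baseline was Grade 1 or below, so DLT counts do not depend on the missing line. SAP Section 2 reports that DL-1 has been opened. At that level Table 4.5.2.1-1 generally ends ulocuplumab at the first drug-related Grade 3 or higher event, so there the difference is nivolumab re-exposure alone.

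**The case against.** The strongest reply is that other rules leave almost nothing open. Much of that stands. Grade 4 bilirubin, the combined rule and the 6-week limit are mandatory at any baseline. Protocol 3.5 also requires a stop when the investigator judges that staying on would not serve the subject ("Any clinical AE, laboratory abnormality or intercurrent illness which, in the opinion of the investigator, indicates that continued participation in the study"). A reader might infer from the missing line that normal-baseline subjects have no bilirubin stop at all, or that everything short of Grade 4 is left to the investigator. The documents do not support either reading, because the combined rule and the 6-week rule bind without discretion. But the combined rule needs raised enzymes, the 6-week rule misses events that recover sooner, and investigator judgment is not a mandatory criterion.

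Appendix 2 also counts for something. Section 4.5.1.2 recommends its algorithms to standardise management across all subjects, and a restart after bilirubin above 5x ULN would go against the footnote's implication. Appendix 2 describes itself as guidance, however, and the figure it annotates is not shown.

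Protocol 6.3 prefers clinical terms to laboratory terms, and a Grade 3 non-skin adverse event lasting over 7 days requires discontinuation. That preference governs how an event is named. It does not turn a bilirubin value into a non-laboratory event.

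Finally, Amendment 04 aligned these criteria with nivolumab programme language, and a tighter bilirubin cap for subjects with abnormal enzymes could be deliberate. The alignment gives an origin for the section but no reason for this line. Sections 1.4.2.1 and 1.5 are not in the text available, so I say only that no reason appears in what can be read.

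**Conclusion.** The omission is real and worth correcting, but it is a minor safety point. It bites only when all of these hold: both enzymes normal at baseline; drug-related bilirubin above 5x ULN and below Grade 4; AST/ALT at or below 3x ULN; recovery to Grade 1 or below or to baseline within 6 weeks, or under a delay exception; and an investigator who chooses to restart. It rests on the assumption that Grade 4 bilirubin starts above 5x ULN; at a cut-off of exactly 5x there is no gap.

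The documents give neither the rate of such events nor the share of subjects with normal baseline enzymes, so no probability can be attached. A reader might also infer that the trial's results are at risk. They are not: DLT counts, endpoints, sample size and analysis are unchanged.

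**What to change.** Add total bilirubin above 5x ULN to the normal-baseline list in Protocol 4.5.3.2, using the wording already in the Grade 1-2 list. Alternatively, move it out of the split and state it once for all subjects. Because this adds a mandatory discontinuation criterion, it needs a protocol amendment with IRB/IEC approval under Protocol 9.1.1. It can go into the next amendment. The cost is one line of text, and that a few subjects may permanently stop nivolumab who would have tolerated a restart. The SAP needs no change.

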#### **4.5.4 Treatment of Ulocuplumab- or Nivolumab-Related Infusion Reactions**

Infusion reactions have been reported in subjects treated with ulocuplumab and nivolumab. If an infusion reaction was to occur, it might manifest with fever, chills, rigors, headache, rash, pruritis, arthralgias, hypo- or hypertension, bronchospasm, or other symptoms. All Grade 3 or 4 infusion reactions should be reported within 24 hours to the BMS Medical Monitor and reported as an SAE if criteria are met. Infusion reactions should be graded according to NCI CTCAE (version 4.0) guidelines.

Treatment recommendations are provided below and may be modified based on local treatment standards and guidelines as appropriate:

**For Grade 1 symptoms** (Mild reaction; infusion interruption not indicated; intervention not indicated):

Remain at bedside and monitor subject until recovery from symptoms. The following prophylactic premedications are recommended for future infusions: diphenhydramine 50 mg IV (or equivalent) and/or paracetamol 325 to 1000 mg (acetaminophen) at least 30 minutes before additional nivolumab or ulocuplumab administrations.

**For Grade 2 symptoms** (Moderate reaction requires therapy or infusion interruption but responds promptly to symptomatic treatment [eg, antihistamines, non-steroidal anti-inflammatory drugs, narcotics, corticosteroids, bronchodilators, IV fluids]; prophylactic medications indicated for  $\leq 24$  hours):

Stop the nivolumab or ulocuplumab infusion, begin an IV infusion of normal saline, and treat the subject with diphenhydramine 50 mg IV (or equivalent) and/or paracetamol 325 to 1000 mg (acetaminophen); remain at bedside and monitor subject until resolution of symptoms. Corticosteroid or bronchodilator therapy may also be administered as appropriate. If the infusion is interrupted, restart the infusion at 50% of the original infusion rate when symptoms resolve; if no further complications ensue after 30 minutes, the rate may be increased to 100% of the original infusion rate. Monitor subject closely. If symptoms recur then no further nivolumab or ulocuplumab will be administered at that visit. Administer diphenhydramine 50 mg IV, and remain at bedside and monitor the subject until resolution of symptoms. The amount of study drug infused must be recorded on the electronic case report form (eCRF). The following prophylactic premedications are recommended for future infusions: diphenhydramine 50 mg (or equivalent) and/or paracetamol 325 to 1000 mg (acetaminophen) should be administered at least 30 minutes before additional nivolumab or ulocuplumab administrations. If necessary, corticosteroids (recommended dose: up to 25 mg of IV hydrocortisone or equivalent) may be used.

**For Grade 3 or Grade 4 symptoms** (Severe reaction, Grade 3: prolonged [ie, not rapidly responsive to symptomatic medication and/or brief interruption of infusion]; recurrence of symptoms following initial improvement; hospitalization indicated for other clinical sequelae [eg, renal impairment, pulmonary infiltrates]; Grade 4: (life threatening; pressor or ventilatory support indicated):

Immediately discontinue infusion of ulocuplumab or nivolumab. Begin an IV infusion of normal saline, and treat the subject as follows. Recommend bronchodilators, epinephrine 0.2 to 1 mg of a 1:1,000 solution for subcutaneous administration or 0.1 to 0.25 mg of a 1:10,000 solution injected slowly for IV administration, and/or diphenhydramine 50 mg IV with methylprednisolone 100 mg IV (or equivalent), as needed. Subject should be monitored until the investigator is comfortable that the symptoms will not recur. Ulocuplumab or nivolumab will be permanently discontinued. Investigators should follow their institutional guidelines for the treatment of anaphylaxis. Remain at bedside and monitor subject until recovery from symptoms. In the case of late-occurring hypersensitivity symptoms (eg, appearance of a localized or

generalized pruritis within 1 week after treatment), symptomatic treatment may be given (eg, oral antihistamine, or corticosteroids).

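### Protocol 4.5.4: the Grade 2 text withholds drug for one visit when an infusion reaction recurs on restart, but the same section defines that recurrence as Grade 3, which requires discontinuation

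*Protocol*

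**What the plan says.** Protocol 4.5.4 manages infusion reactions by grade. For Grade 2, the infusion is stopped, the subject is treated and, once symptoms have gone, the infusion is restarted at half rate. If the reaction comes back: "If symptoms recur then no further nivolumab or ulocuplumab will be administered at that visit". The same paragraph then turns to later dosing: "The following prophylactic premedications are recommended for future infusions: diphenhydramine 50 mg (or equivalent"), and so on. It neither excludes subjects whose symptoms came back nor says that their event changes grade.

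The Grade 3/4 heading that follows describes a Grade 3 reaction. Its descriptors include "recurrence of symptoms following initial improvement; hospitalization indicated for other clinical sequelae". The action for these grades is: "Ulocuplumab or nivolumab will be permanently discontinued".

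Other provisions bear on the same event:

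- Grading (4.5.4): "Infusion reactions should be graded according to NCI CTCAE (version 4.0) guidelines".
- Reporting (4.5.4): "All Grade 3 or 4 infusion reactions should be reported within 24 hours to the BMS Medical Monitor".
- Status of the 4.5.4 text: "Treatment recommendations are provided below and may be modified based on local treatment standards and guidelines as appropriate".
- 4.5.3.1 lists a drug-related infusion reaction of Grade 3 or worse, whatever its duration, as a reason to stop ulocuplumab. 4.5.3.2 does the same for nivolumab at Grade 3.
- 3.5 makes these criteria binding: "Subjects MUST discontinue investigational product (and non-investigational product at the discretion of the investigator) for any of the following reasons". Its list ends with a reference to 4.5.3.1 and 4.5.3.2.
- 3.1.4 counts a drug-related non-hematological AE of Grade 3 or worse in the first 6 weeks as a DLT. It also counts any toxicity managed by discontinuing either drug.

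**The concern.** One event receives two incompatible instructions, and the more permissive one sits where a nurse or investigator would look first, in the paragraph for the grade already assigned. The main stake is patient safety: a subject who has met a mandatory stopping criterion could receive the same antibody again, with premedication.

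The second stake is the DLT count. If the event stays at Grade 2 and the drug is continued, neither the Grade 3 bullet nor the discontinuation bullets of 3.1.4 are met. The Grade 3/4 report to the Medical Monitor is not triggered either, unless the event is also an SAE. Tolerability is decided on 3 to 6 evaluable subjects, so a single event can matter. DL-1 is the level where it still could. SAP section 2 records that DL1 had exceeded its limit and that DL-1 had been opened. Under protocol 3.1.1, an unacceptable DL-1 ends enrollment for that tumor type.

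**Working it through.** The plan states no figure to reproduce. The check compares the texts and then applies the DLT rules.

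**Step 1: does recurrence on restart always meet the Grade 3 wording?** The Grade 2 paragraph allows restart only after symptoms have resolved. Symptoms that return after restart have therefore returned after improvement, which is the Grade 3 descriptor. No subset of the recurrences covered by that sentence stays at Grade 2 on the protocol's own wording.

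**Step 2: the two actions side by side.**

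| | Grade 2 paragraph | Grade 3/4 text, 4.5.3 and 3.5 |
|---|---|---|
| That visit | No more drug | Stop the infusion |
| Later visits | Premedicated infusions, no exclusion | Discontinue the drug to which the reaction is attributed |
| Medical Monitor | No specific report | Report within 24 hours |
| DLT (drug-related, first 6 weeks) | Not triggered | DLT |

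The adverb making discontinuation permanent appears in 4.5.4. Sections 4.5.3.1 and 4.5.3.2 say only that the drug is discontinued. At DL-1, Table 4.5.2.1-1 agrees: a first drug-related event of Grade 3 or worse, outside its listed exceptions, ends ulocuplumab. No text reconciles the two columns.

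**Step 3: would a mis-graded subject still count in the DLT denominator?** Section 3.1.4 needs at least 5 of 6 ulocuplumab and at least 2 of 3 nivolumab doses. Ulocuplumab is always infused first (4.5), and a nivolumab dose blocked by an ulocuplumab reaction is to be replaced (4.5.1.4). With all other doses given, and the affected dose counted as lost:

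- Ulocuplumab reaction at a joint visit: 6 − 1 = 5 of 6 ulocuplumab; nivolumab replaced, 3 of 3.
- Ulocuplumab reaction at an ulocuplumab-only visit: 6 − 1 = 5 of 6; nivolumab 3 of 3.
- Nivolumab reaction: ulocuplumab already given, 6 of 6; nivolumab 3 − 1 = 2 of 3.

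Each case meets both minima, so the subject would generally remain evaluable and be counted as DLT-free.

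**Step 4: effect of one uncounted DLT under 3.1.1.**

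| Evaluable | True DLTs and decision | Counted DLTs and decision | Changed? |
|---|---|---|---|
| 3, 4 or 5 | 1: keep enrolling | 0: tolerable | Yes |
| 3, 4 or 5 | 2: intolerable | 1: keep enrolling | Yes |
| 3, 4 or 5 | 3: intolerable | 2: intolerable | No |
| 6 | 1: tolerable | 0: tolerable | No |
| 6 | 2: intolerable | 1: tolerable | Yes |
| 6 | 3: intolerable | 2: intolerable | No |

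This table holds for any missed DLT. It gives the consequence of a miss and says nothing about how often this wording would cause one.

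**The case against.** The strongest reply is that the two texts can be read together. Withholding drug for the visit is the acute step and does not order later re-dosing. The premedication advice sits under the Grade 2 heading and may be meant only for reactions that stay at Grade 2. The Grade 3 description follows at once, CTCAE grading is required, and 4.5.3 is mandatory, whereas the 4.5.4 text is advice that sites may adapt. Section 7 adds regular safety calls during the DLT period and continuous Medical Monitor review.

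Much of this stands. A reader might infer that sites following the protocol would re-dose these subjects. The documents support only that they could, because a careful investigator would re-grade the event and 4.5.3 would then govern. A reader might also infer that the subject loses both drugs at the visit and sits exactly on both evaluability minima. The dosing order and the replacement rule in 4.5.1.4 do not support that. The DLT consequence also needs several conditions together: relatedness, timing, under-grading, no later correction, and a cohort where one event is decisive.

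What does not stand is that nothing needs correcting. The sentence on recurrence is written for exactly this event, limits the action to one visit, and is followed by advice on future infusions with no exclusion. The allowance for local adaptation does not waive 4.5.3. Monitoring lowers the chance of an undetected miss but leaves the instruction in place, and the Grade 3/4 report depends on the grade that the paragraph leaves unchanged.

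**Conclusion.** The inconsistency is real and should be corrected. As written, 4.5.4 could lead a site to re-dose a subject who meets a mandatory stopping criterion. This rests on the protocol's wording alone and needs no assumed rate.

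The DLT consequence is secondary and conditional. Its frequency cannot be estimated, because the documents give no rate of recurrence on restart. Its size, if it happens, is that of one missed DLT under 3.1.1. The statement that the subject would generally stay evaluable assumes that the other scheduled doses are given.

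A reader might go further and infer that the DL-1 tolerability decision is already compromised. The documents do not support that: they report no recurrent infusion reaction at DL-1 and no mis-graded event at any level.

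**What to change.** Amend the Grade 2 paragraph of 4.5.4 along these lines:

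*If symptoms return after restart, stop the infusion. The reaction is then Grade 3 and is managed under the Grade 3/4 text: permanently discontinue the causative drug, report to the Medical Monitor within 24 hours, and assess as a DLT under 3.1.4 if drug-related and in the DLT period. Premedication for future infusions applies only to Grade 2 reactions without recurrence. Section 4.5.1.4 continues to govern a nivolumab dose blocked by an ulocuplumab reaction, but must not lead to re-dosing of a drug that has been discontinued.*

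The last sentence is needed because 4.5.1.4 refers to the next combined dose without any limit by grade.

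Then check the infusion reactions already recorded in the DLT period, mainly at DL-1. The planned outputs on interrupted infusions (SAP 7.4.2.1) and infusion-related AEs (SAP 7.6.7), with the eCRF record of the amount infused, will find candidates. None of these is described as capturing recurrence after restart, so source records may be needed to confirm it.

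The cost is a few sentences through the ordinary protocol revision process, and a short data check with source review where needed. It requires no SAP change, extra subjects or extra procedures.
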